NCT02753816

Document Date: 07/10/2018

1. TXA Protocol Title: The effect of tranexamic acid on blood loss and transfusion rates in burn wound surgery – A randomized, double-blinded placebo-controlled trial.

2. Version Date: 7/10/18

3. Objectives:

- To determine the impact of perioperative administration of tranexamic acid on intra-operative blood loss and post-operative transfusion rates in burn wound surgery.

4. Background:

An estimated 40,000 patients were hospitalized for burn related injuries in 2014.¹ Many of these patients required surgical excision and grafting. Early excision of burn eschar has been shown to reduce mortality, hospital stay, and time away from work. However, intraoperative blood loss and blood product transfusion rates have been shown to be higher.^{2,3} Tangential excision of burns often causes large losses of blood, which have been estimated between 0.4 ml/cm² to 0.75 ml/cm² of debridement depending on timing of excision.⁴ There are many techniques that have been described to help reduce the loss of blood in burn surgery. These include timing of excision, maintaining euthermia, extremity tourniquet control, dilute epinephrine tumescent infiltration, and topical application of epinephrine and thrombin.^{5,6}

Tranexamic acid (TXA) has been used as an adjuvant to reduce bleeding since the 1960's.⁷ TXA acts by competitively binding to plasminogen leading to inhibition of its activation to plasmin. This is thought to inhibit fibrinolysis, maintain formed clot, and decrease perioperative bleeding.⁸

Topical and intravenous uses of TXA have been studied in a variety of surgical specialties, including orthopedic surgery,⁹ oral surgery,¹⁰ cardiovascular surgery,¹¹ trauma,¹² as well as gynecology.⁷ Impact on blood loss and decreased transfusion needs have been promising. Very little data exist on the use of TXA in burn surgery with only one case report and one prospective trial published.^{13,14} Although a small sample size was used, results were encouraging for decreasing intraoperative blood loss. The effect on perioperative blood transfusion was not addressed in this study.

Due to inhibition of fibrinolysis, a theoretical risk of venous thromboembolic (VTE) events is at the forefront for concern. Numerous studies have shown no increase in VTE events with perioperative use of TXA.^{9,15} Although the reasons are unclear, incidence of VTE within the burn population are quite low (0.8%) compared to many inpatient populations.¹⁶

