- Subject or subject's medical decision maker agrees to participate in this study and provides informed consent

ii. Exclusion Criteria

- Subjects with a history of hypercoagulopathy, deep vein thrombosis or pulmonary embolism
- Baseline creatinine level greater than 2.83 mg/dL
- Subjects with known hypersensitivity to tranexamic acid
- Patients with acquired defective color vision
- Patients with subarachnoid hemorrhage
- Children
- Pregnant women
- Prisoners

b. Study Endpoints

The primary outcome measures will be operative blood loss (measured and calculated) and red blood cell transfusion rates in subjects undergoing the eligible procedures. Secondary outcome measures will include total hospital length of stay, wound complication, transfusion reactions, and skin graft survival.

c. Procedures Involved in the Research

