Interim reviews of unblinded data for statistically significant findings will be performed by an independent clinician, pharmacist, and statistician after the first 80 procedures have been completed. Findings will be reviewed with the investigators, and decisions will be made as to whether or not the research study continues. These interim reviews and outcomes will be reported to the IRB.

f. Withdrawal of Subjects

Subjects will be withdrawn from the study if they experience an adverse drug reaction defined as anaphylaxis. Other potential side effects such as nausea, vomiting, or diarrhea will be treated symptomatically per standard of care. If refractory to standard treatment for these side effects, subjects will be withdrawn from the study. Subjects experiencing any thrombotic event prior to completion of study drug dosing schedule will be withdrawn from study. Subjects may choose at any time to voluntarily withdraw from the study. If subjects choose to withdraw, No further data will be collected. Data already collected will be included in the study.

The primary investigator may remove a subject at any time from this research study if it is felt to be in the best interest of the subject.

8. Statistical Plan

a. Sample Size Determination

The primary outcome variable for the study is transfusion following a procedure. The analysis will be performed using generalized estimating equations (GEEs), as each individual may have multiple surgical procedures that may be randomized to either the control or TXA treatment prior to EACH procedure. An initial assessment for sample size for a McNemar test, assuming that the transfusion rate following a control procedure is 50%, the rate following a TXA procedure is 30%, $\alpha = 0.05$ and $\beta = 0.20$, indicates that 61 subjects would be needed. The control transfusion rate is based upon previous data at Spectrum Health, while the difference of 20 percentage points is based upon our estimate of what constitutes a clinically important effect. Due to the use of GEE for the analysis, a correction factor is needed.¹⁷ From previous data from the Spectrum Health Burn Unit, we assume that there will be three procedures per patient. If we further assume that the intraclass correlation coefficient = 0.8 (postulated correlation of repeated measurements), we will be able to show a statistically significant effect with 53 subjects. With an average of 3 procedures per patient, the total procedures will be 159.

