b. **Statistical Methods**

Summary statistics will be calculated. Quantitative data will be expressed as the mean±SEM and nominal data will be expressed as a percentage. Comparisons between groups for quantitative variables will be performed using the t-test. Nominal variables will be evaluated using the χ^2 test. The relationship between TXA administration and transfusion will be determined using GEE. Significance will be assessed at $p<0.05$. Analyses will be performed using intention to treat.

9. Risks to Subjects

TXA is an FDA approved medication. The safety of TXA has been demonstrated in a meta-analysis of the off-label use of TXA in the perioperative period. A theoretical risk of thromboembolic events exists, though no significant adverse outcomes have been reported with the proposed dosing schedule. Reported side effects include nausea, vomiting, diarrhea, and dizziness. Uncommon side effects include allergic dermatitis, giddiness, and hypotension. Rare side effects include blood clots, convulsions, and visual changes.

10. Potential Benefits to Subjects

Potential benefits include decreased surgical blood loss resulting in decreased transfusion requirements. Transfusion of packed red blood cells has been associated with numerous potential adverse events. In addition, decreased overall hospital cost may occur if the study subjects experience decreased complication rates.

11. Provisions to Protect the Privacy Interests of Subjects

The study, potential risks and benefits of treatment will be discussed extensively with each potential subject preoperatively in a private space. Any questions they have will be answered accordingly. Reported data will not contain identifiable information. Patient consent and all other research related activities will take place in a private exam room.

12. Provisions to Maintain the Confidentiality of Data

Identifiable study data will be kept in a secure password-protected file or locked cabinets by the Spectrum Health OCRO. The Spectrum Health OCRO will have record of the randomization of each individual subject stored in a controlled, secure area.

13. Medical Care and Compensation for Injury

Any medical or surgical complications experienced relative to this research will be treated in accordance with current standards of care. No study funds have been set aside to compensate subjects for injury.

14. Cost to Subjects

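### Section 7b makes blood loss and transfusion both primary, Section 8a names and sizes transfusion alone, and no rule says what counts as success

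*Combined protocol and SAP*

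**What the plan says.** Section 7b (Study Endpoints) reads: "The primary outcome measures will be operative blood loss (measured and calculated) and red blood cell transfusion rates". Its next sentence lists the secondary outcomes, and blood loss is not among them.

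Section 8a (Sample Size Determination) reads: "The primary outcome variable for the study is transfusion following a procedure". The only planning effect is on transfusion, 50% on control against 30% on TXA. No effect size, standard deviation or power is given for blood loss.

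Section 8b (Statistical Methods) names a method for transfusion: "The relationship between TXA administration and transfusion will be determined using GEE". Blood loss is not named there and falls under a general sentence: "Comparisons between groups for quantitative variables will be performed using the t-test". One significance threshold, p < 0.05, covers everything.

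Section 3 (Objectives) names both outcomes, blood loss first: "intra-operative blood loss and post-operative transfusion rates in burn wound surgery". Section 7e plans "Interim reviews of unblinded data for statistically significant findings" after 80 procedures, without saying on which outcome.

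**The concern.** A trial needs one unambiguous statement of what makes it positive. Here the endpoint section and the statistical section answer differently, and neither gives a decision rule. Someone relying on Section 7b could call a significant blood-loss result a primary success when transfusion is not significant, without departing from the written plan. That claim would rest on an outcome for which the trial has no stated power. If any listed primary could carry the claim, the overall false-positive rate would exceed the stated 5%.

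The number of primary tests is also unclear. Measured and calculated blood loss may be one variable or two, so the count is two or three.

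The conflict reaches the interim review as well. Those looking at unblinded data cannot tell whether significant blood loss with non-significant transfusion is a primary finding.

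**Working it through.** **1. The plan's own figure.** Inputs from Section 8a: 61 subjects by McNemar, 3 procedures per patient, intraclass correlation 0.8.

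- 61 × [1 + (3 − 1) × 0.8] / 3 = 61 × 2.6 / 3 = 52.87, rounded up to 53.
- 53 × 3 = 159 procedures.

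Both match the plan. The starting 61 depends on a discordant-pair proportion that the plan does not give; about 0.318 to 0.323 returns 61 two-sided. That is a separate gap. What matters here is that every input concerns transfusion.

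**2. Familywise error if any one listed primary counts.** Assumptions: each test is a valid two-sided 5% test (the plan does not state sidedness), there is a single look, and the test statistics are multivariate normal under the null with an assumed common correlation r. For independent tests the error is 1 − 0.95^k:

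- two tests: 1 − 0.95² = 0.0975
- three tests: 1 − 0.95³ = 0.1426

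Correlated cases come from numerical integration with critical value 1.96.

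**3. Chance of a false blood-loss-only result favouring TXA.** This is P(any Z > 1.96) − 0.025. At r = 0 it is 1 − 0.975² − 0.025 = 0.0244 for two tests and 1 − 0.975³ − 0.025 = 0.0481 for three.

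| r | Familywise error, 2 tests | Familywise error, 3 tests | Blood-loss-only, 2 tests | Blood-loss-only, 3 tests |
|---|---|---|---|---|
| 0 | 9.75% | 14.3% | 2.4 points | 4.8 points |
| 0.3 | 9.5% | 13.6% | 2.3 points | 4.3 points |
| 0.5 | 9.1% | 12.5% | 2.0 points | 3.8 points |
| 0.7 | 8.35% | 10.9% | 1.7 points | 3.0 points |
| 0.9 | 7.0% | 8.4% | 1.0 point | 1.7 points |

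With the two blood-loss versions correlated at 0.7 and each at 0.5 with transfusion, simulation gives 12.0% and 3.5 points.

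The interim look and the use of a t-test on repeated procedures from the same patient are not counted in these figures.

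**4. Cost of an equal alpha split.** Taking 80% power at 53 subjects at face value, the noncentrality is 1.960 + 0.842 = 2.802.

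- Two tests (alpha 0.025, critical value 2.241): power = Φ(2.802 − 2.241) = 71%. Size factor (2.241 + 0.842)² / 2.802² = 1.211, so 53 × 1.211 = 64.2, or 65 subjects.
- Three tests (alpha 0.0167, critical value 2.394): power = Φ(2.802 − 2.394) = 66%. Factor 1.334, so 53 × 1.334 = 70.7, or 71 subjects.

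Working instead through the McNemar formula with the implied discordant proportion of 0.323 gives 71% and 65 subjects for two tests, and 65% and 72 subjects for three.

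**5. If all primaries had to succeed.** Type I error would be at most 5%. Joint power could not exceed the 80% planned for transfusion, and it cannot be calculated because blood loss has no planning figures.

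**The case against.** The best defence is that Section 8 governs inference. Section 8a uses the singular, gives transfusion the only assumed effect and sizes the trial on it, and Section 8b gives it the only outcome-specific analysis. Section 7b would then merely list outcomes of interest, and there would be no multiplicity among primaries. This is a plausible reading, but nothing in the documents adopts it. It requires setting aside the section that defines the endpoints and separates primary from secondary.

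The inflation also depends on a rule the plan does not contain. Section 7b joins the outcomes with a conjunction, and an all-must-succeed reading would control the error. That is right, and it is why the figures are conditional. Likewise, the three-test figures apply only if measured and calculated blood loss are tested separately. Independence is the upper end of the range, since blood loss and transfusion in the same procedure are plausibly correlated. At r = 0.9 with two tests, the false blood-loss-only risk is only 1.0 point.

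These arguments limit the size of the problem. They do not supply the missing rule, and each reading leaves either Section 7b or Section 8a in need of correction.

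**Conclusion.** The concern holds, and the plan must be corrected. Sections 7b and 8a give conflicting primary outcomes in current text, and no passage reconciles them or defines success. If any one listed primary counts, familywise error at a single look runs from 7.0% to 9.75% for two tests and from 8.4% to 14.3% for three, over assumed correlations from 0.9 down to 0. It is above 5% at every correlation examined. If transfusion alone is confirmatory, there is no inflation among the primaries, but Section 7b is then wrong as written.

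**What to change.** In Section 7b, name transfusion as the sole primary outcome, in line with Section 8a and the sample size. Then either list measured and calculated blood loss as secondary, or state in Section 8b that they are tested in a prespecified order and only after transfusion is significant. Either route leaves 53 subjects, 159 procedures and alpha 0.05 unchanged and holds the error across these outcomes at the stated level, apart from the interim look, which needs its own rule.

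The cost is that a blood-loss-only result can no longer be called a primary success, although the title and Section 3 name blood loss first. If the sponsor wants blood loss to carry a primary claim by itself, an equal alpha split would allow it, at the loss of power or extra subjects shown above. Requiring all primaries to succeed is also coherent, but needs planning figures for blood loss.

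While editing, Sections 3, 7b and 8a should say whether intra-operative units count as transfusion and when the window ends, and confirm that the 50% control rate uses that definition ("The control transfusion rate is based upon previous data at Spectrum Health"). This is a lesser clarification, and the conclusion does not depend on it.

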The study design will be a randomized, double-blinded, placebo-controlled trial, with the randomization to occur on a per procedure basis. Following satisfaction of inclusion/exclusion criteria and enrollment into the study by the Spectrum Health OCRO research staff, the subject and each procedure the patient undergoes will be assigned a study number. A single consent will be obtained for randomization of each procedure that a patient may undergo meeting inclusion criteria for the study. A single study participant could potentially be randomized to both treatments of the study if that participant undergoes two or more procedures. Each procedure a participating subject undergoes will be randomized based on a predetermined randomization schedule, created by an independent statistician at Grand Rapids Medical Education Partners (GRMEP) research department. The randomization schedule will be held by the pharmacists and checked prior to each procedure to determine the appropriate treatment (placebo or TXA). Surgical timing will be coordinated with the OCRO. The study participants will receive preoperative intravenous TXA or Normosol as placebo treatment. The preparation will be indistinguishable by nursing, surgical, or anesthesia staff. The TXA procedures will receive a 1000 mg dose immediately preceding surgical incision administered by the anesthesia provider, while the placebo procedures will receive an equivalent volume of Normosol. The dose will be administered via intravenous piggyback over 15 minutes. Operative details will be recorded including procedure performed, IV fluids received, estimated blood loss, lowest recorded body temperature, and transfused blood products. Perioperative hemoglobin level data will also be collected. Standard daily laboratory measurements will continue unless clinical conditions necessitate more frequent monitoring, per standard practice. Transfusion will take place for hemoglobin levels < 7.0 g/dL or hemoglobin level < 10 g/dL with clinical symptoms indicating need for transfusion, per standard practice. Final decision on transfusion will be made according to the staff surgeon's discretion.

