It is anticipated that each patient will receive an average of three major surgical procedures during the treatment of their burn injury. The number of procedures may range from a single procedure to greater than 6 procedures for an individual patient depending on the extent of their injury. The time between subsequent procedures typically ranges from ten days to several weeks. Prior to each procedure, the patient will be re-randomized to receive TXA or placebo.

Data to be recorded includes patient demographics (age, sex, height, weight), burn injury characteristics (total body surface area, location, depth of burn), hospital admission date, hospital discharge date, past medical history, past surgical history, medications, and laboratory values. Data from operative records will include procedure date, procedure performed, wound measurements, lowest body temperature, operative blood loss, operative time, amount of fluid received, and intraoperative transfusion requirements. Postoperative data to be collected includes hemoglobin and hematocrit levels, transfusion requirements, surgical complications, skin graft survival (%), thromboembolic events, and length of hospital stay.

d. Data Management

The Spectrum Health OCRO research staff will collect outcome data at the time of each surgical procedure. Data will be stored in a password-protected REDCap

database. The OCRO will also keep a secure record of the procedures randomized to the TXA and placebo arms, which will be blinded from the study personnel.

e. Provisions to Monitor the Data for the Safety of Subjects

Adverse events including infections, allergic reactions, graft loss, respiratory failure, anaphylaxis, thromboembolic events and development of acute renal failure will be monitored and recorded at the time of occurrence by the Spectrum Health OCRO research staff. In the event an increased number of unanticipated events occur, the study will be temporarily stopped pending review. A review of unblinded data will be performed by an independent clinician and statistician at Grand Rapids Medical Education Partners to determine the need to discontinue or resume the study. If a significant increase in adverse events is noted in the treatment arm related to the study drug, the trial will be terminated. Decisions resulting from the review will be discussed with the primary investigator.

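### Total hospital stay is one value per patient but is to be compared between procedure-level arms; analyze it with one record per patient, adjusted for the number of procedures

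*Combined protocol and SAP*

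**What the plan says.** All references are to the combined protocol and SAP.

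- **Endpoint (7b, Study Endpoints).** "Secondary outcome measures will include total hospital length of stay", followed by three further outcomes.
- **Data (7c, Procedures Involved in the Research).** The recorded items include "hospital admission date, hospital discharge date, past medical history", so there is one start date and one end date. The postoperative items in the same section end with "skin graft survival (%), thromboembolic events, and length of hospital stay", with no start point given.
- **Unit of randomization (7c).** The trial is randomized, "with the randomization to occur on a per procedure basis". It follows that "A single study participant could potentially be randomized to both treatments of the study".
- **Procedures per patient (7c).** The average is three, and "The number of procedures may range from a single procedure to greater than 6 procedures for an individual patient". Gaps typically run from ten days to several weeks.
- **Analysis (8b, Statistical Methods).** "Comparisons between groups for quantitative variables will be performed using the t-test". GEE is named only for transfusion.

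The documents do not say which procedure or arm a stay is assigned to, or how a patient treated in both arms is counted. They also leave open whether all of a patient's procedures fall in one admission.

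**The concern.** Followed as written, 8b compares stay between TXA procedures and placebo procedures. A patient with one TXA procedure and two placebo procedures then supplies the same number of days to both groups, and supplies it three times. For a later procedure, part of that stay has already passed before the dose is given.

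A shorter hospital stay is among the benefits hoped for at the end of section 4 (Background), so readers will look at this result. At stake are three things: what the reported difference means, how precise it is, and whether the mean stay shown for each arm describes the patients in the trial.

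**Working it through.** **The plan's own figure.** No figure is given for stay. The sample size in 8a reproduces: 61 × [1 + (3 − 1) × 0.8] / 3 = 52.87, so 53 patients, and 53 × 3 = 159 procedures. These counts are used below.

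**1. Share of patients whose one stay enters both arms.** Assume independent 1:1 assignment (the ratio is not stated) and one admission. With k procedures the share is 1 − 2 × 0.5^k.

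| k | Share in both arms |
|---|---|
| 1 | 0% |
| 2 | 50% |
| 3 | 75% |
| 6 | 96.9% |

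The formula is concave in k, so at a mean of three and 1:1 allocation 75% is the ceiling. If k varies around that mean (assumed shapes), the share is 61% for 1 to 5 equally likely, 63% for 1 + Poisson(2) and 50% for a geometric distribution. With 2:1 allocation and k = 3 it is 67%.

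**2. What the t-test estimates.** Assumed inputs: 53 patients; k from 1 to 5, equally likely; stay = 5 + 10k days, SD 8; each TXA dose shortens stay by 2 days. In simulation the procedure-level difference averaged −1.96 days against a true −2 per dose, and with no effect the t-test rejected about 5% of the time. Because each procedure is assigned independently of the patient's others, sharing a stay does not bias the contrast for one assignment. For a three-procedure patient, TXA throughout changes stay by 3 × (−2) = −6 days, which the contrast does not show directly.

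**3. Precision of the t-test.** On average half of the procedures receive TXA, so expected stay is 5 + 10k − 2(k/2) = 5 + 9k. Over procedures, a patient counts k times.

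- Mean of k over procedures = E(k²)/E(k) = 11/3 = 3.67.
- Variance of k over procedures = E(k³)/E(k) − 3.67² = 15 − 13.44 = 1.56.
- Variance of stay over procedures ≈ 81 × 1.56 + 64 + 3.7 = 194, so SD 13.9. The 3.7 is the part from the number of TXA doses, 4 × k/4 at k = 3.67.
- SE = 13.9 × √(4/159) = 2.2 days.

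**4. Precision of a patient-level regression.** Regress stay on the number of TXA procedures, adjusted for k. Given k, the number of TXA procedures has variance k/4, on average 0.75. SE ≈ 8 / √(53 × 0.75) = 1.27; simulation gives 1.3 days.

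**5. Power for −2 days per dose.** t-test: Φ(1.96/2.21 − 1.96) = Φ(−1.07) = 14%. Regression: Φ(2.0/1.3 − 1.96) = Φ(−0.42), about 33%. With geometric counts the SEs are 4.9 and 1.3 days.

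**6. Where the gain comes from.** If every patient has exactly three procedures, the simulated SEs are 1.32 for the t-test and 1.30 for the regression, so the gain is gone. Keeping all procedure records and only adding k as a covariate also gives 1.30. The loss is due to unadjusted variation in k, not to the shared stay.

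**7. Mean stay.** Over procedures: 5 + 9 × 3.67 = 38.0 days (37.9 in simulation). Over patients: 5 + 9 × 3 = 32.0. With equal k the two coincide.

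**The case against.** The best defense is that the planned test works for what randomization by procedure can answer. It is essentially unbiased for one assignment and holds its error rate. The regression proposed below also reports an effect per TXA procedure, so it does not target a different quantity. Its advantage depends on stay rising with the number of procedures, and the 10 days per procedure is assumed. All of this stands, and it limits the point to precision, description and a missing definition.

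Several stronger readings are tempting, and the documents do not support them.

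- **That the comparison cannot show any effect on stay, because the within-patient difference is zero.** Under independent re-randomization, step 2 shows otherwise. It would come true if assignments were balanced within patients, but the schedule is not described that way.
- **That 75% of patients count in both arms.** This needs exactly three procedures each; 7c gives three only as an average.
- **That the analysis forces a null result.** An exchangeable GEE at high correlation would shrink the estimate toward zero, but 8b assigns GEE to transfusion only.
- **That the shared stay causes the imprecision.** Step 6 shows it does not.

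It can also be said that 7c lists stay among postoperative data, which might mean stay after each procedure. But 7b says total stay. The two wordings are a further reason to define the variable.

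**Conclusion.** The point holds in limited form. A patient-level endpoint is sent to a procedure-level t-test with no unit of analysis and no attribution rule. With independent 1:1 allocation and one admission, about half to three quarters of patients would enter the same stay in both arms. The result would be a valid but often imprecise estimate of one assignment's effect, not the effect of a TXA-treated course. Where stay rises with the number of procedures, the arm means would describe heavily operated patients more than the average patient.

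The sizes (SE 2.2 against 1.3 days, power 14% against 33%, mean stay 38 against 32 days) rest on assumed stay figures and show scale only. With no spread in the number of procedures, the differences in precision and in mean stay disappear. This is a secondary endpoint, and the primary analysis is unaffected. The change is worth making because it is cheap.

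**What to change.** In 7b, define total stay as a patient-level outcome, and say how readmissions are counted. In 8b, take it out of the procedure-level t-test. Analyze one record per patient: regress total stay on the number of randomized procedures given TXA, adjusted for the number of randomized procedures. Report the effect per TXA procedure, and report mean stay per patient.

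**Cost.** Wording only; dates and allocations are already recorded. The analysis has 53 records instead of 159, which step 4 shows does not lose precision. The real downside is that the number of procedures is known only after randomization and could itself be affected by TXA, for example through graft survival. The result should therefore be labeled supportive.

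**Check free of that problem.** Compare stay from the first randomized procedure to discharge by that first assignment. It is imprecise. With total stay as a stand-in and the same assumptions, the patient-level variance is 81 × 2 + 64 + 3 = 229, so SD 15.1 and SE = 15.1 × √(4/53), about 4.2 days. It can support the regression but not replace it.
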